5.6 Sample Attrition

Figure 1 describes household attrition through midline.

5.6.1 Baseline attrition

Attrition between randomization and baseline can be attributed to household non-response, inability to locate sample households, households no longer meeting eligibility criteria for the study, and missing baseline data. Randomization accounted for the most updated tracking data from the baseline survey; however, a lag contributed to overall attrition between randomization and baseline.

[figure not shown]

Figure 1: Attrition through midline.

5.6.2 Midline attrition

Attrition between baseline and midline can be attributed to household non-response and the inability to locate sample households, including their movement outside the village. Since many households with missing baseline data were able to be surveyed at midline, a total of 10,111 randomized households have midline data, an attrition rate of 7% between randomization and midline.

6 Companion willingness-to-pay study

We conducted a Willingness-to-Pay study (WTP study) that is distinct from but complements the main experiment. In some of our specified analyses, we will use the data from this companion study.

After conducting the listing exercise explained in Section 5.3.1, we selected a random subsample of 210 households, 105 from each district, to participate in the WTP study. Each of these households met the inclusion and exclusion criteria laid out in Section 5.1. However, these households were then excluded from selection for the main study, i.e., the treatment assignment described in Section 5.2. Instead, these 210 households were administered the baseline survey and a survey that used the Becker-DeGroot-Marshak (BDM) mechanism to measure the household's willingness to pay for RSBY health insurance. (These elicitations were incentivized, i.e., those households whose stated WTP was above the random draw in the BDM procedure received RSBY coverage at their stated WTP.)

7 Identification Strategy

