5.2 Treatment assignment

We designed a two-stage randomization process to study both direct treatment and spillover effects of health insurance.

In a first stage, we randomly assigned villages to one of five village-level arms. A village-level arm is defined by the percentage of households within the village assigned to each of the four household-level study arms defined in subsection 4.2.1. The percentage allocations to the 4 household-level arms are given in the last 4 columns of Table 1. The percent of villages assigned to each of the 5 village-level arms are in the second column. Villages were matched before this first stage randomization.⁷

Table 1: IHIE Two-Stage Randomization Design

Village-level arms (%)		Household-level arms (%)			
Arm	Village allocation	Group A	Group B	Group C	Group D
I	15	30	50	10	10
II	15	30	10	50	10
III	15	30	10	10	50
IV	35	70	10	10	10
V	20	10	30	30	30
Total	100	40	20	20	20

In a second stage, we randomly assigned households within a village to the four arms according to the allocation probabilities assigned to the village. Households were matched before this second stage randomization.⁸

The target enrollment for each of the 4 household-level arms, unconditional on village-level arm, was 4,500 households for condition A and 2,250 households for each of conditions B, C and D. Due to some attrition between listing and completion of baseline, our final randomized sample amounted to 11,089 households in 424 villages in the two districts.

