7.5 Minimizing attrition bias

We address the possibility that attrition affects our ITT or CATE estimates in the following manner. Let a_{ijk} be an indicator that equals 1 if our data contain a non-missing observation on household i in village j at baseline but not at endline. First, we check balance in attrition across household or village treatment arms by estimating the ITT model in equation (2) while setting $y_{ijt} = a_{ij}$. We will also test whether there is differential attrition across insured and uninsured households by estimating system (3) while setting $y_{ijt} = a_{ij}$.

Second, if we find evidence of differential attrition, we will take either of two approaches. One is to impute outcomes for attrited households using multiple imputation (King et al. 2001). In this approach, we will compare ITT and CATE effects with imputation and without. The other approach is to bound our parameter of interest using Lee bounds (Lee, 2009).

If we observe differential attrition, we will estimate all of our regressions with a correction for sample selection inspired by DiNardo, Fortin, and Lemieux (1996). Their procedure re-weights the data using the inverse of the propensity to be observed at endline, so that the distribution of observable characteristics at baseline among households observed at endline resembles that in the entire baseline sample.

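### The attrition indicator in section 7.5 cannot register the loss of a randomised household that has no baseline data; separately, the midline rate of 7% does not match the readable counts

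*Combined protocol and SAP*

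**What the plan says.** **Attrition rule.** Section 7.5 sets the indicator to 1 when "our data contain a non-missing observation on household i in village j at baseline but not at endline". The indicator is then the outcome in the ITT model, equation (2), and in the enrolment model, system (3). If differential attrition is found, the plan uses multiple imputation or Lee bounds. It also re-weights every regression so that the baseline characteristics of households seen at endline match those of the whole baseline sample.

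**Households without baseline data.** Section 5.6.1 lists among the causes of loss "households no longer meeting eligibility criteria for the study, and missing baseline data". Section 5.6.2 says that "many households with missing baseline data were able to be surveyed at midline". Section 5.3.6 sets out whom to interview at endline in such households. Section 7.1 (Control variables) begins with a regression without controls, which needs no baseline data.

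**Midline count.** Section 5.2 states that "our final randomized sample amounted to 11,089 households in 424 villages in the two districts". Section 5.6.2 reports that "a total of 10,111 randomized households have midline data, an attrition rate of 7% between randomization and midline". According to section 5.6, "Figure 1 describes household attrition through midline"; that figure is not in the text available for review.

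**The concern.** The differential-attrition test is a gate: imputation, bounds and re-weighting follow only if it shows a problem. It should therefore be able to detect loss among all households that the ITT analysis is meant to represent. Households without baseline data belong to the randomised sample and can contribute endline outcomes. Their loss at endline happens after assignment and could differ by arm, but the indicator never takes the value 1 for them.

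A second gap appears if re-weighting is triggered. The weights rest on baseline characteristics, and the target is the baseline sample, so households without baseline data have no defined weight. The weighted and unweighted ITT estimates could then describe different households.

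The midline figure is a smaller matter. The stated rate and the two stated counts all refer to randomisation, yet they do not agree.

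**Working it through.** **1. The plan's own figure.** Inputs: 11,089 randomised (section 5.2); 10,111 with midline data and 7% attrition (section 5.6.2).

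- Loss: 11,089 − 10,111 = 978, and 978/11,089 = 8.8%. The 7% is not reproduced.
- With 10,111 fixed, a rate that rounds to 7% needs a denominator between 10,111/0.935 and 10,111/0.925, that is 10,814 to 10,930. This is 159 to 275 below 11,089.
- With 11,089 fixed, it needs 10,258 to 10,368 households at midline, 147 to 257 more than stated.
- Other denominators: the target of 4,500 + 3 × 2,250 = 11,250 gives 10.1%, and the rounded 11,000 gives 8.1%. Subtracting the 210 willingness-to-pay households gives 768/10,879 = 7.06%, but section 6 places those households outside the treatment assignment, so the text does not support that subtraction.

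**2. How section 7.5 codes each type of randomised household.**

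| Baseline data | Endline data | Indicator | Lost from the randomised sample? |
|---|---|---|---|
| yes | yes | 0 | no |
| yes | no | 1 | yes |
| no | yes | 0, or left out | no |
| no | no | 0, or left out | yes |

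Read literally, the definition gives 0 in the last row. Read as limited to the baseline sample, it omits the last two rows. Either way the loss in the last row does not register.

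**3. How many households are affected.** This cannot be derived. Section 5.2 introduces the 11,089 with "Due to some attrition between listing and completion of baseline", which suggests that the count is already net of baseline loss. Section 5.6.1 says that "a lag contributed to overall attrition between randomization and baseline", which suggests further loss afterwards.

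**4. Illustration of size (inputs assumed).** This is a simple comparison of arms A and D without clustering. It is not the planned test, which uses equation (2) with village shares, their interactions with arm, and village-clustered HC2 errors. Section 7.5 sets no numerical trigger, so z = 1.96 is also an assumption.

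- Arm sizes from the Table 1 totals: A = 0.4 × 11,089 ≈ 4,436; D = 0.2 × 11,089 ≈ 2,218.
- At an assumed 10% loss, SE = √[0.09 × (1/4,436 + 1/2,218)] = 0.0078, and 1.96 × SE = 1.53 percentage points.
- Let m be the share without baseline data, and b and g the A-versus-D gaps in endline loss among households with and without baseline data. The full gap is (1 − m)b + mg.
- The g needed for the full gap to reach 1.53 points is (1.53 − (1 − m)b)/m.
- Left-out reading: the tested gap is b, with threshold 1.53/√(1 − m).
- Coded-0 reading: the tested gap is (1 − m)b. The pooled rate is p = 0.10 × (1 − m), and the threshold is 1.96 × √[p(1 − p)(1/4,436 + 1/2,218)].

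| m (households) | g needed, b = 0 | g needed, b = 1.2 | Left out: gap v threshold, b = 1.2 | Coded 0: gap v threshold, b = 1.2 |
|---|---|---|---|---|
| 2% (222) | 76 | 18 | 1.20 v 1.54 | 1.18 v 1.52 |
| 5% (554) | 31 | 8 | 1.20 v 1.57 | 1.14 v 1.49 |
| 10% (1,109) | 15 | 4.5 | 1.20 v 1.61 | 1.08 v 1.46 |

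Gaps and thresholds are in percentage points. With b = 1.2, neither reading of the planned indicator crosses its threshold, while the full gap would do so at the g shown. With b = 0, the omitted households would need a very large gap of their own.

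**The case against.** **Different purposes.** Section 5.6.2 gives a descriptive midline rate and section 7.5 defines an endline test variable, so a reader might infer a contradiction that is not there. This stands: different starting sets are not in themselves an inconsistency. The defect lies within section 7.5, between its indicator and the sample that the ITT can use.

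**Order of events.** On the stated dates the baseline survey (August 2013 to February 2014, section 5.3.2) preceded randomisation (August 2014) and disclosure of assignment (May and June 2015, section 5.4). A reader might infer that assignment caused the missing baseline data, or that the planned test is invalid. The dates do not support either inference: the test is sound for the households observed at baseline. But endline loss among the other households still occurs after assignment, and nothing tests it.

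**Missing figure.** Figure 1 may show an exclusion or denominator that yields 7%, and section 5.6.1 does mention households that ceased to be eligible. This also stands. A reader might infer that the true rate is 8.8% and that attrition was understated; the readable text shows only that the three figures disagree. Figure 1 may also give the total without baseline data.

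**Lee bounds need no baseline covariates.** True, so the undefined-weight problem concerns re-weighting only. The bounds are still reached only through the same test.

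**Conclusion.** The main point holds: under either reading, the section 7.5 indicator cannot register the loss of a randomised household seen at neither baseline nor endline, although it controls whether any correction is made. This rests on the wording of the plan and not on Figure 1.

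Its size is unknown. The illustration suggests that it matters mainly when the gap among baseline-observed households is already near the threshold or when close to 10% of households lack baseline data. It does not show that the endline estimates will be biased.

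The midline discrepancy is a reporting matter that feeds no test. A reader might infer that the trial has lost more households than it was powered for. The documents do not support that, because 8.8% is still within the 10% allowance in section 5.1.

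**What to change.** **Section 7.5.** Replace the definition with: *the indicator equals 1 if household i in village j was randomised and has no endline data, and 0 if it was randomised and has endline data.* Then:

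- Run the differential-attrition test over all randomised households and keep the baseline-observed version as a secondary check.
- Base any eligibility exclusion only on criteria fixed at the 2013 study start or on data recorded before assignment. Status after assignment should not be used: holding a BPL card is an exclusion in section 5.1, but holding one now is an outcome in section 8.3.3, so a later eligibility check could condition on an effect of treatment.
- If re-weighting is triggered, target the full randomised sample, using the listing variables that already served to block households (section 5.3, footnote 8) where baseline data are missing.
- Report by arm how many randomised households lack baseline data.

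**Sections 5.2 and 5.6.2.** Reconcile 11,089, 10,111 and 7%, either by stating the denominator and exclusions behind 7% or by restating the rate as 8.8%.

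**Cost.** A recode, a second run of the attrition model, a slightly more complex weight model, one count by arm and a clarifying sentence. No new data are needed. The stated midline attrition may become slightly less favourable.

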7.1 Intent-to-Treat (ITT)

Our first parameter of interest is the ITT estimate of the impact of different forms of access to insurance (free, at cost, etc.). Our basic regression model to estimate this is:

$$y_{ijt} = \sum_{v=1}^5 \beta_v d_j^v + \sum_{h=1}^3 \gamma_h d_{ij}^h + \sum_{h=1}^3 \sum_{v=1}^5 \lambda_{hv} d_j^v d_{ij}^h + \delta X_{ijs} + e_{ijt} \quad (1)$$

where y_{ijt} is the outcome for household i in village j at time t ; d_j^v is the indicator for village group $v \in \{1, 2, 3, 4\}$, corresponding to I, II, III, IV and V village groups; d_{ij}^h is the indicator for household

group $h \in \{1, 2, 3, 4\}$; γ_h for $h \in \{1, 2, 3\}$ are ITT estimators for adding one household to groups A, B, and C (D is the baseline); and (β_v, λ_{hv}) measures spillovers.

Coding treatment variables. In order to facilitate interpretation of village group, we estimate an isomorphic specification that recodes the village groups variables, $(d_j^{v=1}, \dots, d_j^{v=5})$, to reflect share of village sample in arms A, B, C, and D, $(\sigma_j^1, \dots, \sigma_j^4)$. The mapping from village group indicators to arm shares is given by the last four columns of Table 1. So, for example, the indicator for village group 1, $d_j^{v=1}$, maps to $(\sigma_j^1, \sigma_j^2, \sigma_j^3, \sigma_j^4) = (0.3, 0.5, 0.1, 0.1)$. Our modified regression model is now:

$$y_{ijt} = \sum_{h=1}^4 \beta_h \sigma_j^h + \sum_{h=1}^3 \gamma_h d_{ij}^h + \sum_{h=1}^3 \sum_{h'=1}^4 \lambda_{hh'} \sigma_j^{h'} d_{ij}^h + \delta X_{ijs} + e_{ijt} \quad (2)$$

where σ_j^h is the proportion of group $h \in \{1, 2, 3\}$ or $\{A, B, C\}$ in village j . Unlike the nonparametric approach given in equation (2), this equation is based on a parametric assumption. However, this specification increases power as it has fewer parameters to be estimated and allows for extrapolation regarding the effects of varying treatment proportions (see Appendix E.1 of [name], Jiang, and [name] (2019)).¹⁰

In addition, we will estimate two substantively different specifications to abstract away from methods of access to insurance and towards the mere fact of access to insurance. On one, we replace the four household group indicators with an indicator for whether the household was in group A, B or C and we replace the four village-level arm share variables with the share in groups A, B or C.¹¹ Additionally, we will estimate a specification where σ_j^v is replaced by the total share of the village eligible for RSBY, including both the share assigned to A, B and C as well as the share of the village with BPL cards or in certain eligible occupational classifications (who were therefore RSBY eligible).

Control variables. We first estimate a variant of the regression model above without any controls X_{ijs} , where s indicates a time that may not be equal to t . We then estimate a specification where X_{ijs} is a vector of baseline controls (i.e., X_{ijs} at time $s = 0$). We will use machine learning methods to select these control variables. Finally, we will run specifications where X_{ijs} may include so-called “coloring variables” that shed light on mechanisms of impact, welfare effects, and the dosage of treatment. In the latter case, we will include interactions of treatment variables with coloring variables, the same manner in which we estimate heterogeneous treatment effects. These coloring variables are listed in section 8.

Weighting. This regression can be weighted in multiple ways. We could either weight each household equally or weight each village arm identically. When examining household-level access We choose to weight each household equally because no household is obviously more informative than any other, especially when examining questions about the impact of insurance on households. When examining spillovers, we will weight villages equally.

Standard errors. We use the cluster robust HC2 standard errors at the village level. [name], Jiang, and [name] (2019) shows that this is a conservative variance in two-stage randomized experiments.

Spillovers. To address the possibility of spillovers from, e.g., giving some households access to insurance in one way affects households not given access to insurance in that way, we do a few things.

First, we measure ITT effects accounting for spillovers at the village level by examining the predicted effects on outcomes for a household in a given group at different shares of the village sample in that group. The specific shares selected could be in-sample shares or out-of-sample shares. We will highlight when we make out-of-sample predictions.¹² In cases where we want to report ITT under sample average spillovers, we will exclude interaction between household arms and, e.g., village arms.

Second, we make assumptions required for unbiased estimation of, (γ_h, λ_{hv}) with spillovers as given in [name], Jiang, and [name] (2019). The key assumption is partial non-interference, i.e., assignments in villages $j' \neq j$ do not influence outcomes in another village j .

Third, to test for the existence of spillover effects, we conduct the Wald test with the null hypothesis that $\beta_v = \beta_{v'}$ and $\lambda_{vh} = \lambda_{v'h}$ for any $v \neq v'$ and $h = 1, 2, 3, 4$. This test can be conducted for both take-up and any outcome variable of interest.

¹⁰<https://imai.fas.harvard.edu/research/files/spillover.pdf>.

¹¹Berry et al. (2018) consider different subsidies and associated extrapolation issues.

¹²Although our study varies the fraction of subjects in a village who receive access to insurance in some form, we do not – as Table 1 shows – give some treatment to no households or some treatment to all households. Therefore, to estimate the above parameter of interest we have to make out-of-sample predictions.

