5.4 Treatment Delivery

The population that is eligible for this study would not be eligible for RSBY under the program's usual rules. To make this study possible, we exchanged letters of cooperation with the state in which we conducted the study (Karnataka), the central government agency (Ministry of Labor) responsible for administration of RSBY, and the development organization (GIZ) providing technical support for RSBY.

Sample households were randomized in August 2014 using data from the listing exercise. They were informed of their treatment assignment and, depending on which arm to which they are assigned, given access to insurance or cash in May and June 2015. This step took place roughly 18 months after the baseline due to government constraints. Due to challenges associated with evaluating a government program, we were only able to enroll sample households when the government held its RSBY enrollment drive in early 2015.

We enrolled study households much in the same way the government enrolled RSBY (non-study) eligible households into the program: via a mobile enrollment truck that visited each village. One difference is that we went to each household to ask them if they would like to enroll and took them to the enrollment truck, which was parked in one place in the village. By contrast, the government informed non-study households by delivering paper notices (chits) to each home about when and where the enrollment truck would be in the village.

Roughly 78.4%, 70.4% and 58.6% of households in arms A, B, and C, respectively enrolled in RSBY. Enrollment rates are somewhat higher in Gulbarga than Mysore: 77.9/76.4/64.1% v. 78.8/63.5/52.3% in A/B/C. No one in arm D enrolled.

For all study households that take up insurance, we paid the government their premiums. For households in arms A, this was funded by grant funds. For those in B and C that purchase insurance, this was funded by the respondents' money.

The Karnataka government renewed RSBY automatically for non-study and study households in 2016 and 2017 without any action—even payment—by enrollees. RSBY ended in the state on August 31, 2018, to make way for the new NHPS scheme, which is scheduled to start in late 2018 or early 2019. As of this writing, Karnataka had agreed to roll out NHPS but had not begun the roll-out.

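### The ITT coefficient γ_h is not identified in equations (1) and (2) as printed, and the plan names neither the headline version of the ITT nor the village mix at which it is read

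*Combined protocol and SAP*

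**What the plan says.** Section 7.1 makes the ITT effect of each form of access its first target and says that the γ_h "are ITT estimators for adding one household to groups A, B, and C (D is the baseline"). In equation (1) both the village main effects and the interactions run over v = 1 to 5, "corresponding to I, II, III, IV and V village groups", although the index set printed beside it stops at 4.

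Equation (2) recodes the village groups "to reflect share of village sample in arms A, B, C, and D". "The mapping from village group indicators to arm shares is given by the last four columns of Table 1". All four shares enter as main effects and in each interaction, yet the share is then defined only for A, B and C. No omitted category or constraint is stated for either equation. Equation (4) in section 7.3 has an intercept and three uncentred shares.

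The Spillovers part of section 7.1 gives two ways to report an ITT: predicted effects at selected in-sample or out-of-sample shares, and a model without the interactions when the ITT is wanted at the sample's average level of spillover. It adds "We will highlight when we make out-of-sample predictions".

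For attrition, section 7.5 says "we check balance in attrition across household or village treatment arms by estimating the ITT model in equation (2"). Section 7.1 says the spillover Wald test can be applied to take-up; section 5.4 reports "No one in arm D enrolled".

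**The concern.** A coefficient called the ITT should have one meaning, fixed in advance. Here the printed models leave γ_h undetermined, and the meaning depends on which column the analyst or the software removes. Each choice gives a different estimand. Some are effects in one village group only, and some are effects in a village mix that the trial never created. At stake are the definition and precision of the plan's first parameter, and the attrition check, whose result decides whether imputation, bounds or reweighting are used.

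**Working it through.** **Inputs.** Table 1 (section 5.2), set out with village arms as columns, in per cent:

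| | Arm I | Arm II | Arm III | Arm IV | Arm V |
|---|---|---|---|---|---|
| Villages | 15 | 15 | 15 | 35 | 20 |
| Share in A | 30 | 30 | 30 | 70 | 10 |
| Share in B | 50 | 10 | 10 | 10 | 30 |
| Share in C | 10 | 50 | 10 | 10 | 30 |
| Share in D | 10 | 10 | 50 | 10 | 30 |

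Sample: 11,089 households in 424 villages, about 26 each (equal village sizes assumed). Outcome SD is set to 1. The ICC is not in the plan; 0 to 0.05 is assumed.

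**1. Reproduce the plan's own totals.** For A: 0.15×30 + 0.15×30 + 0.15×30 + 0.35×70 + 0.20×10 = 40. B, C and D each come to 20. This matches the Total row.

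**2. Rank.** In equation (1) the five indicators sum to 1, so for each h the five interaction columns add up to d_ij^h. Adding a constant to every λ_hv and subtracting it from γ_h leaves the fit unchanged.
- Equation (1): 5 + 3 + 15 = 23 columns; there are only 5 × 4 = 20 cells; rank 20.
- Equation (2): 4 + 3 + 12 = 19 columns; the four shares also sum to 1; rank 16.
- Each is short by exactly 3, one for each γ_h.
- The part of equation (4) without w has 16 columns and rank 16, so it is identified.

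**3. What γ_h becomes after a normalisation.**
- Equation (1) with village arm v omitted from the interactions: the effect in village arm v only.
- Equation (2) with the D share dropped, or equation (4) at w = 0: the effect where the A, B and C shares are all zero, that is, a 100%-D village. The largest D share in Table 1 is 50%.

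**4. Standard errors at ICC 0.** The plain difference has SE = √(1/n_h + 1/n_D).
- A: n = 11,089×0.4 = 4,436 against 2,218, giving 0.0260.
- B or C: 2,218 against 2,218, giving 0.0300.

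For example, B in village arm V has 11,089×0.20×0.30 = 665 households against 665. SE = √(2/665) = 0.0548, and 0.0548/0.0300 = 1.83. For the share models the SE comes from the diagonal of (X′WX)⁻¹ over the 20 cells. Ratios to the plain difference:

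| Version of γ_h | A | B, C |
|---|---|---|
| No interactions | 1.11 | 1.07 |
| Equation (2), shares centred at 0.4/0.2/0.2 | 1.20 | 1.21 |
| Equation (1), one village arm omitted | 2.09–3.44 | 1.83–3.65 |
| D share dropped (all-D village) | 0.1348/0.0260 = 5.18 | 0.1788/0.0300 = 5.95 |

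**5. Clustering.** With a village-clustered sandwich variance and ICC 0–0.05, the all-D ratios are 4.7–5.2 (A) and 5.7–6.0 (B, C). The centred version runs from 1.09 to 1.21.

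**6. Illustrative power.** Section 5.1 gives a 25% change and 10% attrition, but no base rate, alpha, power or ICC. Take C against D with 2,250×0.9 = 2,025 per arm, a 25% increase and two-sided 5%. Plain-difference power is 41%, 60%, 80% and 97% at base rates of 5%, 8%, 12% and 20%. At 12% the standardised effect is 1.96 + 0.84 = 2.80. Dividing by 5.95 gives 0.47 and power of about 8%; by 1.21, about 64%; by 1.07, about 75%.

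**7. Take-up Wald test.** In equation (1) without controls, each β_v is the arm D mean in village group v. For 2015 enrolment every such mean is exactly zero with zero variance, so the joint covariance matrix is singular. The null also names h = 4, for which equation (1) has no λ. The λ contrasts for A, B and C remain testable.

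**The case against.** The strongest reply is that section 7.1 already provides usable routes. Predicted effects at stated shares are the same whichever column is dropped. The no-interaction model is full rank and, at ICC 0, more precise than centring (1.07–1.11 against 1.20–1.21). Footnote 12 admits that no treatment goes to none or all of a village's households. This stands: the trial can estimate an ITT, and the fault lies in the printed equations and the label on γ_h.

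Four stronger readings are tempting, and the documents do not support them:
- That the headline result will depend on software column order. This holds only if someone reports the raw γ_h from the interacted model and ignores the Spillovers text.
- That the trial has about 8% power. That figure belongs to one coefficient that the Spillovers text does not select, and the 80% beside it comes from an assumed base rate.
- That the attrition check is nearly powerless. Section 7.5 names the model but no single coefficient; a joint test of equal attrition across all arms does not depend on the normalisation.
- That collinearity breaks the spillover Wald test. Contrasts of λ between village groups are estimable. The take-up difficulty has a separate cause, zero enrolment in arm D.

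The reply does not settle which route is the headline or which mix is the reference. The Spillovers text itself still treats γ_h and λ_hv as estimable without a normalisation. The promise to flag out-of-sample predictions would not obviously reach a coefficient already labelled ITT.

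**Conclusion.** The point holds as a specification error. The rank deficit is exact algebra from Table 1 and needs no outcome data. Read with the D share dropped, γ_h is an extrapolation to a village mix outside the design, with a standard error about five to six times that of the plain difference. That size applies to the all-D coding only and rests on equal village sizes and an assumed ICC of 0–0.05. Under equation (1) the ratio at ICC 0 is 1.8 to 3.7. Dropping the B or C share in equation (2) instead gives up to 7.3, so six is not an upper limit. Section 7.1 partly repairs the problem but leaves the headline version and reference mix open, and equation (4) and the section 7.5 check keep the interacted form. All power figures are illustrative.

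**What to change.** 1. Name the no-interaction γ_h as the headline ITT, and state that it is an average over village arms.
2. Where interactions are kept in (2) and (4), use an intercept, drop the D share and centre the others (A − 0.4, B − 0.2, C − 0.2), so that γ_h is the effect at the average village mix.
3. In (1), omit the separate γ_h and report the sum over v of w_v λ_hv with w = 0.15, 0.15, 0.15, 0.35, 0.20. Correct the printed index sets.
4. In section 7.5, test household-arm differences in attrition with the no-interaction or centred form, or with a joint test that does not depend on the normalisation, and say which.
5. Separately, restrict the spillover Wald test for 2015 take-up to the contrasts in arms A to C, and remove h = 4 from the null.

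The cost is a revision of wording and recoded regressors. No new data are needed.

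### Equation (2) is a linear restriction of equation (1), not a recoding of it, and the no-access prediction rests on that untested linearity

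*Combined protocol and SAP*

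**What the plan says.** Equation (1) in Section 7.1 has an indicator for each of the five village arms, for household arms A, B and C, and for their products. Under *Coding treatment variables* the plan then states: "we estimate an isomorphic specification that recodes the village groups variables". On the recoding it says: "The mapping from village group indicators to arm shares is given by the last four columns of Table 1".

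The same paragraph continues: "Unlike the nonparametric approach given in equation (2), this equation is based on a parametric assumption". The equation number in that sentence must be a slip for (1). The paragraph also says that "this specification increases power as it has fewer parameters to be estimated and allows for extrapolation".

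Under *Spillovers*, ITT effects are to be predicted for a household in a given group "at different shares of the village sample in that group". The shares may lie inside or outside the sample, and predictions outside it will be highlighted. Footnote 12 notes that no treatment was given to none or to all of a village's households, and adds: "Therefore, to estimate the above parameter of interest we have to make out-of-sample predictions".

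**The concern.** An isomorphic model would give the same fitted cell means under other labels. A model with fewer parameters that permits extrapolation does not, so the paragraph contradicts itself. A reader who takes the label at face value will not see that a testable restriction has been imposed.

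The restriction carries weight because a village without access is the natural benchmark for the total effect of insurance including spillovers, and Table 1 contains no such village. The largest arm D share is 50%, so the benchmark lies 50 points beyond the data and is reached only through linearity in shares. The Wald test in Section 7.1 asks whether spillovers exist, not whether they are linear. No lack-of-fit test, alternative functional form or limit on extrapolation is given.

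The contrast is also incompletely defined. The four shares sum to 1, so one share cannot move unless another does, and the plan does not say which.

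**Working it through.** **Inputs.** Village allocation and shares come from Table 1 (Section 5.2). The 424 villages are from Section 5.2. Enrolment of 78.4%, 70.4%, 58.6% and 0% in arms A to D is from Section 5.4. Equal village weighting for spillovers is from Sections 7.1 and 11.1.

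**1. Table 1 reproduces.** Arm A: 0.15 × (30 + 30 + 30) + 0.35 × 70 + 0.20 × 10 = 40. Arm B: 0.15 × (50 + 10 + 10) + 0.35 × 10 + 0.20 × 30 = 20. C and D also give 20. These match the Total row.

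**2. The shares are linearly dependent.** 0.5 × (I + II + III − IV) gives, for A, 0.5 × (0.3 + 0.3 + 0.3 − 0.7) = 0.1. For each of B, C and D it gives 0.5 × (0.5 + 0.1 + 0.1 − 0.1) = 0.3. That is row V exactly, so the five rows have rank 4.

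**3. Model dimension.** There are 5 × 4 = 20 cells. Equation (1) has 5 + 3 + 15 = 23 columns and rank 20, so it is saturated. Equation (2) has 4 + 3 + 12 = 19 columns and rank 16. Within every household arm it forces

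mean(V) = 0.5 × [mean(I) + mean(II) + mean(III) − mean(IV)],

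which is four restrictions in all.

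**4. Illustration (assumed shape).** Let the spillover on D households equal squared village enrolment, where village enrolment is 0.784A + 0.704B + 0.586C. Fit the four shares by least squares with village weights 15/15/15/35/20.

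| Village arm | Enrolment | True D mean | Equation (2) fit | Residual |
|---|---|---|---|---|
| I | 0.646 | 0.417 | 0.415 | 0.002 |
| II | 0.599 | 0.358 | 0.356 | 0.002 |
| III | 0.364 | 0.133 | 0.130 | 0.002 |
| IV | 0.678 | 0.459 | 0.460 | −0.001 |
| V | 0.465 | 0.217 | 0.220 | −0.004 |

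The in-sample range is 0.459 − 0.133 = 0.33 (rounded).

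- No access (D = 100%): predicted −0.245, truth 0. The error is 0.245 / 0.327 = 75% of the range.
- All-A: predicted 0.58, truth 0.784² = 0.61. The error is about 0.03.
- The pooled model in Section 7.1, using the share in A, B or C, predicts −0.293 for no access.

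**5. Precision.** The no-access prediction puts weights −0.572, −0.572, 1.928, −0.428 and 0.644 on arms I to V. Its SE is √(Σ a²/n), with n = 63.6, 63.6, 63.6, 148.4 and 84.8 villages and equal variance assumed. That gives 0.274 SD of a village-level mean.

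- Average mix: 0.0486, ratio 5.6.
- Raw arm III mean: 0.125, ratio 2.2.
- Fitted arm III value: 0.115, ratio 2.4.

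**6. What a lack-of-fit test would see.** The contrast in step 4 is 0.2166 − 0.5 × (0.4171 + 0.3583 + 0.1326 − 0.4594) = −0.008. Its SE is 0.159 SD, so 80% power (two-sided 5%, one household arm) needs a departure of about 0.45 SD. The illustration would reach that only if the village-level SD were below 0.0077 / 0.445 = 0.017. Moreover, a full quadratic in three free shares has 10 coefficients and the five arms fix only 5. Five independent quadratic terms are therefore exactly zero at every arm, and no test on these data can see them.

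**7. Displaced group.** Moves within Table 1 that raise A by 40 points change village enrolment as follows.

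- D displaced (III to IV): 0.4 × 0.784 = 31 points.
- C displaced (II to IV): 0.4 × (0.784 − 0.586) = 8 points.
- B displaced (I to IV): 0.4 × (0.784 − 0.704) = 3 points.

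**The case against.** Much is already in place. Equation (1) is the basic model and is saturated. The spillover Wald test is written in village-group terms, and Section 11.1 compares outcomes within each household arm by village stratum, so detecting spillovers does not depend on equation (2). The plan states the parametric assumption, promises to highlight out-of-sample predictions and concedes them in footnote 12. It adds a pooled access-share model, in which the displaced group is D by construction, and a model using the total eligible share of the village. It nowhere makes 0% or 100% access a headline result. All of this stands, and it limits the point to a wrong label, a missing diagnostic, an undefined contrast and unprotected extrapolation. The pooled model does not supply that protection, as step 4 shows.

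A reader might go further in three ways that the documents do not support.

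- *Full-access predictions are as unreliable as no-access ones.* In the well-fitting illustration all-A is nearly right. Larger full-access errors with a perfect fit can be constructed, for example with curves that flatten exactly at the edge of the design, but nothing in the plan points to such curves.
- *The estimates are shown to be biased.* The plan gives no spillover shape. The squared curve shows what a good fit can hide, not what happened.
- *A lack-of-fit test settles the matter.* Step 6 shows that passing it does not validate the extrapolated predictions. Using it to choose between the equations would add a data-dependent model choice.

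**Conclusion.** The point holds. By Table 1, equation (2) is nested in equation (1) with one restriction per household arm, so the label is wrong and conflicts with the rest of its own paragraph. This part is algebra and needs no assumption. No planned test covers the restriction.

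The practical exposure is mainly the no-access prediction. Under an assumed squared-enrolment spillover it misses by about three quarters of the observed range while every arm fits within 0.004. The SE ratios assume 424 villages split as in Table 1, equal weights and equal village-level variance. Predictions at the Table 1 mixes rely only on the four testable restrictions and are much less exposed. This is a gap in wording and sensitivity analysis, not concealment and not a fault in the randomised comparison.

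**What to change.** In Section 7.1:

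- Describe equation (2) as restricted (linear in shares), and correct the reference to the nonparametric approach so that it points to equation (1).
- Report the 4-df lack-of-fit test and the equation (1) cell estimates beside equation (2) results, as a diagnostic and not as a rule for choosing the model.
- Whenever a share is varied, name the group displaced, and use shifts that are feasible within Table 1, such as arm III to arm IV (A up 40 points, D down 40, B and C held).
- Report any no-access or full-access prediction as a sensitivity result beside at least one nonlinear form, such as a quadratic in village enrolment. State that passing the lack-of-fit test does not validate it.

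The cost is a few lines of text, one further Wald test and one alternative fit. No new data are needed. Extrapolated estimates will be presented less firmly.
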